4.8 Early termination of the investigation

The Sponsor, DMC, or CEC may terminate the investigation prematurely according to certain circumstances, for example:

- ethical concerns,
- insufficient subject recruitment,
- when the safety of the subjects is doubtful or at risk, respectively,
- alterations in accepted clinical practice that make the continuation of the investigation unwise,
- early evidence of benefit or harm of the experimental intervention.

4.9 Clinical investigation plan amendments

Substantial amendments are only implemented after approval by the CEC. The use of waivers from the CIP is prohibited (Annex XV, Chapter 2, Art. 3.10 MDR).

Under emergency circumstances, deviations from the CIP to protect the rights, safety and well-being of the subjects may proceed without prior approval by the Sponsor and the CEC. Such deviations shall be documented and reported to the Sponsor and the CEC within 2 days.

All non-substantial amendments are communicated to the CEC together with the Annual Safety Report (ASR). The ASR shall include any deviations from the CIP that may have affected the rights, safety or well-being of the subject or the scientific integrity of the investigation (ISO14155:2020).

All protocol amendments will be submitted to the CEC when any revision is made to the original protocol or subsequent version of the protocol that significantly affects the safety of subjects and/or any change is made that significantly affects the scope of investigation or scientific quality of the study.

The amended protocol will be reviewed, approved and documented by the same method in which the original protocol was reviewed and approved. Once the amended protocol and all associated documents are reviewed and approved, the protocol number and effective date will be changed on the title page.

The final approved amended protocol will be distributed to participating investigator(s) at each site.

4.10 Deviation from the Clinical Investigation Plan

The use of waivers from the CIP is prohibited (Annex XV, Chapter 2, Art. 3.10 MDR). Investigators are not allowed to deviate from the clinical investigation plan. Under emergency circumstances, deviations from the CIP to protect the rights, safety and well-being of human subjects may proceed without prior approval of the Sponsor and the CEC. Such deviations shall be documented and reported to the Sponsor and the CEC as soon as possible, but in no event later than 5 working days after the emergency occurred.

CIP deviations are to be reported in the deviation/violation log provided with the investigator site file and the CRF. Serious CIP deviations are to be reported in writing with the corresponding log to the Sponsor and the CEC within 24 hours. Investigators will be retrained by the Sponsor or its representative. Investigators not complying with the protocol might be disqualified from participation in the clinical trial at the discretion of the Sponsor.

5. BACKGROUND AND RATIONALE

5.1 Background and Rationale for the clinical investigation

5.1.1 Background and Rationale for Hypoxic Blood:

Red blood cells (RBCs) comprise the only tissue in the body that provides oxygen transport. Anemia results from either the acquired loss of RBCs due to disease, injury, or surgery or the inability of the patient to produce their own RBCs due inherited disorders. While the overall clinical settings of anemia can differ greatly between acute or chronic causes, the primary therapeutic goal of RBC transfusion is to increase the oxygen-carrying capacity and prevent tissue hypoxia¹. Red blood cells can be stored for up to 42 days before transfusion but, surprisingly, there are few quality parameters that predict the efficacy and safety of a transfusion².

5.1.2 Consequences of Current RBC Storage Process

A review of the literature^{2,3,4,5} identifies substantial evidence suggesting decreased quality of RBCs from substances that accumulate during RBC storage. These include nitric oxide (NO) scavengers and inhibitors of NO generation that affect vascular tone, procoagulant microparticles, free and non-transferrin bound iron, and bioactive lipids. Additionally, RBCs show progressively diminished deformability over time, characteristics necessary to adequately perfuse the microcirculation⁴. D'Alessandro and colleagues observed significant changes in the plasma levels of hemolytic markers,

oxidized purines, plasticizers, and oxidized lipids in recipients of blood stored for 42 days, compared with 5 days³.

Yoshida and colleagues performed an exhaustive review of the oxidative and metabolic changes that occur to RBCs during storage, summarizing elements of the RBC storage lesion from causes to associated clinical sequelae. The review identifies root causes, effects on RBCs, physiological consequences reported from in vitro experiments or animal models, and finally, potential clinical sequelae of RBC transfusion, each element being identified with its pertinent reference(s)².

5.1.3 Hypoxic storage and HEMANEXT product

Hypoxic storage, where the oxygen content of RBC units is reduced to low levels (e.g., less than 20% oxy-hemoglobin (SO₂)⁶ prior to refrigeration and maintained throughout storage, was proposed as an alternative to antioxidant-based additive solutions to reduce oxidative stress during hypothermic RBC storage^{5,7-11}. The rationale for implementing hypoxic storage is to reduce oxygen, the essential substrate for hemoglobin oxidation that generates the multitude of untoward physiologic and biochemical events described previously.

Hypoxic storage was also shown to counteract some metabolic impairments without requiring novel additive ingrdients^{5,7} independent of the reduction in oxidative stress. During pre-storage processing to reduce oxygen content in the RBC, carbon dioxide is also reduced. Carbon dioxide depletion increases cytosolic pH that was lowered from its physiological level by exposure to acidic anticoagulant and additive solutions. The resulting more neutral pH in the early phase of storage results in sustained flux through the glycolytic pathway and elevated 2,3-DPG levels, which are highly sensitive to pH and normally depleted early during hypothermic storage^{7,11,12}. Additionally, deoxyhemoglobin causes metabolic modulation to release glycolytic enzymes, such as phosphofructokinase and glyceraldehyde dehydrogenase, sequestered at the band 3 binding domain, thereby enhancing overall glycolytic flux during hypoxic storage^{13,14}.

Metabolomics work by D'Alessandro et al has shown that hypoxic storage diminishes damaging mediators of oxidative stress and increases energy biomarkers without requiring novel additive ingredients¹⁵. The same group investigated the metabolomics of hypoxic storage in a two-arm cross-sectional clinical study. Hypoxic storage was found to ameliorate the metabolic phenotypes of stored RBCs (lower markers of oxidant stress such as lipids and purines and higher levels of high-energy phosphate compounds) and improve post-transfusion recovery (PTR). The study also correlated metabolic parameters to hemolysis and PTR, highlighting the role of purine and lipid oxidation (e.g., hypoxanthine and 9-HODE), so that these can be used as markers in fresh and stored units to predict end of storage blood quality¹⁵.

5.1.4 Background on Blood Use in Burn Patients:

Major burn trauma has been found to trigger an inflammatory cascade of events which leads to oxidative stress and tissue damage. These injurious responses, which include complement activation, excessive histamine release, decreased blood pressure, and release of reactive oxygen species, may ultimately lead to the development of multiple organ dysfunction¹⁶. Cardiac dysfunction and acute kidney injury, for example, have been well described as sequelae of burn injury and contribute to multi-organ failure^{17,18,19}.

Early excision and grafting of large burn wounds is currently performed to attenuate the post-burn hypermetabolic state and remove the biological nidus for infection, thereby reducing the risk of burn wound sepsis. These operative procedures can result in considerable bleeding. In one report, intraoperative blood loss was estimated at approximately 9.2% of blood volume for every 1% of total body surface area (TBSA) burn excised²⁰. Burn surgeons also report progressive development of microvascular bleeding and evidence of coagulopathy requiring plasma and platelets as well as RBC transfusions²¹. Coagulopathic bleeding post-op can continue for several days, requiring additional transfusions.

Pasch and colleagues compared estimated blood loss for TBSA burns > and < 20% to provide insight for transfusion ratios for the coagulopathy of burns and also to illustrate the importance of blood loss as a benchmark in these patients to improve care²².

Table 1

Estimated Blood loss (ml/cm ²) for Excision/Grafting		24 hours post-operative EBL Mean ml/cm ² (Std Dev)	72 hours post-operative EBL Mean ml/cm ² (Std Dev)
Total cases	N=66	1.49 (2.16)	1.98 (2.65)
TBSA >20%	N=37	1.08 (1.52)	1.80 (1.87)
TBSA<20%	N=29	2.00 (2.64)	2.20 (3.34)
With Tourniquet	N=11	1.11 (1.34)	2.21 (1.64)
W/O Tourniquet	N=55	1.57 (2.31)	1.92 (2.83)

Table 2 below illustrates number of units of RBCs transfused per TBSA burn as published by different authors.

Author	%TBSA	Units RBCs transfused		
Posluszny and Gamelli ⁸	>10% TBSA	Average 19.7 units (range of 0 to 201 units		
Vasko et al ⁹	>10% TBSA	Average of 8.94 units		
	>30% TBSA	Mean 17 units transfused		
Palmieri et al ¹⁰	≥20% TBSA.	Average 13.7 ± 1.1 units		
	≥50% TBSA	>30 units of blood transfused per patient		
	<10% TBSA	4 ± 0.6		
Yogore et al ¹¹	11 to 19% TBSA	8 ± 1 units		
	20 to 40% TBSA	12 ± 3 units		
	>40% TBSA	20 ± 4 units		

Table 2: Blood Loss During Excision and Grafting

5.1.5 Background on Blood Use in Hematological Malignancies:

Hematologic malignancies such as myelodysplastic syndromes (MDS), multiple myeloma, and leukemia are increasing in prevalence in Norway as the population average age continues to increase. Collectively, hematologic malignancies refers to various disorders of the bone marrow which result in abnormal blood cell production. Leukemia consists of several malignant disorders that present with increased numbers of leucocytes in the blood and bone marrow²³. Multiple myeloma is characterized by uncontrolled growth of plasma cells in the bone marrow. MDS consist of bone marrow diseases associated with ineffective hematopoiesis, resulting in morphologically abnormal blood cells²⁴. In all cases, anemia can result from the overcrowding or ineffective production of normal blood cells, leading to inadequate oxygen delivery.

Patients with hematologic malignancies often require regular blood transfusions at some time during their treatment to alleviate the symptoms of severe anemia, which can include fatigue, weakness, and exacerbation of other underlying medical conditions. While treatment varies with disease severity, transfusions are given at approximately weekly intervals in intensive treatment²⁵. In relying on stored donor RBCs to address anemia, the goal is not to rapidly rebuild a normal red cell mass, but to minimize morbidity and mortality with the lowest possible exposure²⁶. No consensus exists on the appropriate time to commence transfusions or on the correct transfusion threshold for optimal care. Some studies show reduced survival with increased transfusion density²⁷. Iron overload, a consequence of transfusion

dependency, is also independently associated with poor outcomes for patients with MDS^{28,29}. Iron overload with organ impairment may be fatal in those who are heavily iron-overloaded³⁰. Therefore, where a patient has no fatigue-induced limitation on quality of life or function at home, a more conservative approach may be preferred to avoid potential adverse effects and improve outcomes³¹.

[figure not shown]
5.1.6 Potential Benefits of Hypoxic Blood

In vitro and pre-clinical data support the hypothesis that hypoxic blood carries the potential to benefit patients suffering from burn injuries.

Reduce Oxidative stress: Hypoxic storage was initially proposed as an alternative to antioxidantbased additive solutions to reduce oxidative stress during hypothermic RBC storage^{5,7-11}. The rationale for implementing hypoxic storage is to reduce oxygen, the essential substrate for hemoglobin oxidation that generates the multitude of untoward physiologic and biochemical events described previously.

Metabolomics work by D'Alessandro et al has shown that hypoxic storage diminishes damaging mediators of oxidative stress and increases energy biomarkers without requiring novel additive ingredients¹⁵. The same group investigated the metabolomics of hypoxic storage in a two-arm cross-sectional clinical study. Hypoxic storage was found to ameliorate the metabolic phenotypes of stored RBCs (lower markers of oxidant stress such as lipids and purines and higher levels of high-energy phosphate compounds) and improve post-transfusion recovery (PTR). The study also correlated metabolic parameters to hemolysis and PTR, highlighting the role of purine and lipid oxidation (e.g., hypoxanthine and 9-HODE), so that these can be used as markers in fresh and stored units to predict end of storage blood quality¹⁵.

[figure not shown]
Improve Oxygen Delivery: The FDA Clinical Investigation CLIN-0001, which compared conventional blood to hypoxically stored blood at the end of storage (Day 42), demonstrated that hypoxically stored blood showed improvements in ATP, 2,3 DPG, and RBC deformability³². Deformability was evidenced by higher morphology scores in the hypoxic group as well as by higher flow rates by microvascular analysis³³, depicted in Figure 1.

The increases in 2, 3 DPG levels, which remained significantly higher than conventional blood throughout storage, contribute to a rightward shift of the O₂ dissociation curve (i.e., a higher p50), as illustrated by Whitley and colleagues below³⁴.

Reduce Resuscitation Volume/Time: A pre-clinical animal model of resuscitation from hemorrhagic shock with hypoxically stored blood demonstrated clear improvement over conventional blood resuscitation³⁵. Hypoxically stored blood reduced the volume needed to achieve resuscitation by ~50% and reduced time to resuscitation. (The hypoxic group animals were resuscitated in 45 minutes compared to the conventional group animals who never reached the endpoint of 90% mean arterial pressure (MAP) after one hour) Lactate, a diagnostic and therapeutic indicator of shock and acidosis, was cleared faster, and markers of kidney damage (BUN, *u-NGAL*) were reduced with hypoxically stored blood. In summary, hypoxic storage dramatically improved resuscitation efficacy and reduced the volume capable of achieving resuscitation.

Decrease number of RBC transfusions: D'Alessandro et al¹⁵ highlighted that Hemanext exceeded regulatory requirements for hemolysis and post-transfusion *in vivo* recovery (PTR24) by a significant margin. PTR24 values in healthy volunteers were statistically greater for Hemanext RBCs compared to control (90.2% vs 87.3%; p < 0.05)¹⁵. These data illustrate that hypoxic storage yields significantly more viable RBCs and the aforementioned PTR24 is the highest 24-hour recovery reported in the literature. The increase in viable RBCs supports a potential 15% reduction in blood requirements for chronic transfusion patients as well as potential reduction in RBC transfusions for acutely bleeding patients. Wendel et al have discussed the decrease in hemoglobin increment with RBC transfusions that occurs in patients with multiple co-morbidities who experience a systemic inflammatory response³⁶. Burn patients, who are highly inflamed, may therefor experience even greater benefits from hypoxic blood.

[figure not shown]
Decrease Iron Overload: Transfusion iron overload is directly associated with the number of RBC units transfused⁹. Several studies illustrate that hypoxic storage yields more viable RBCs, as indicated by greater PTR24 values⁵. The increase in viable RBCs supports a potential reduction in blood requirements for chronic transfusion patients, potentially leading to lower transfusion density and decreased risk of iron overload.

Summary: In burn patients, hypoxic RBC transfusions can be provided early in resuscitation if there is concomitant trauma, during excision and grafting, and during the post-op period of coagulopathic "oozing". Hypoxic blood presents the potential to alleviate oxidative stress, improve oxygen delivery, and improve resuscitation efficiency with fewer RBC transfusions. The clinical ramifications that may be observed include decreased organ dysfunction in these critically ill patients as well as reduction in thromboembolic events secondary to the improved deformability of the cells. In patients with hematological malignancies, hypoxic RBC transfusions can be provided in the management of anemia and resulting symptoms. Hypoxic blood presents the potential to alleviate oxidative stress and improve oxygen delivery with fewer RBC transfusions. The clinical ramifications that may be observed include decreased density of transfusions and decreased incidence of iron overload, which could improve outcomes for patients who receive chronic transfusions.

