7. CLINICAL INVESTIGATION OUTCOMES

7.1 Primary Outcome

Primary Outcome – for both patients groups

Number of participants who experienced an adverse event (all types/grades) within a time frame up to 24 hours following the transfusion and overall up to 7 days (+/- 1 day) after the transfusion.

The type and the grade of each adverse event will be categorized according to:

- Association for the Advancement of Blood and Biotherapies (AABB) technical manual, 20th edition (2020)
- Biomedical Excellence for Safer Transfusion (BEST) Collaborative review Lancet 2016; 388: 2825–36
- Local AEs database (for reference)
- ISO 14155-2020 definitions

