8.2.3 Other methods for minimising bias

Not applicable. This clinical investigation does not include a comparator.

8.3 **Unblinding Procedures (Code break)**

Not applicable. This clinical investigation does not include a comparator.

CLINICAL INVESTIGATION POPULATION 9.

9.1 **Eligibility criteria**

9.1.1 **Inclusion Criteria**

- A. Hematological malignancies patients group:
 - 1. Patients > 18 years of age
 - Patients expected to require > 2 unit of red blood cells in a single transfusion event

 - 5. Diagnosis of leukemia, myelomatosis or MDS requiring chronic transfusions
- B. Burn patients group:
 - 1. Patients > 18 years of age
 - 2. Patients who have the capacity to consent by themselves to participate to the clinical investigation
 - 3. Smaller burn patients, hospitalized with a Total Body Surface Area (TBSA%) burn ≥ 10% less and \leq than 50%
 - 4. Patients expected to require \geq 2 unit of red blood cells in a single transfusion event

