11.2.1 Assessment of primary outcome

Patients will be monitored for adverse events throughout the entirety of their participation in the clinical investigation. Investigators will monitor patients directly for adverse events during their transfusion visit. In addition, patients will be contacted by phone 24 hours and 7 days (+/- 1) after their transfusion visit to record any adverse events they have experienced since their transfusion visit. All adverse events will be recorded in the CRF and they will be assessed according to the instructions in section 12 of the CIP.

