11.3.4 First Follow-Up Visit

This visit will occur 24 hours post-transfusion and will be performed over the phone. The following data will be collected:

- Infection occurrence
- Adverse event occurrence
- Concomitant medications
- Device deficiencies
- Patient Diary

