11.3.5 Second Follow-Up Visit

This visit will occur 7 days (+/- 1) post-transfusion and will be performed over the phone. The following data will be collected:

- Infection occurrence
- Adverse event occurrence
- Concomitant medications
- Device deficiencies
- Patient Diary

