12. SAFETY

12.1 Definition and Assessment of (Serious) Adverse Events and other safety related events

Adverse Event (AE) (Art. 2 Abs 57 MDR)

Any untoward medical occurrence, unintended disease or injury or any untoward clinical signs (including an abnormal laboratory finding) in subjects, users or other persons whether or not related to the medical device.

Serious Adverse Event (SAE) (Art. 2 Abs 58 MDR)

Any adverse event that led to any of the following:

- (a) death,
- (b) serious deterioration in the health of the subject that resulted in any of the following:
 - (i) life-threatening illness or injury,
 - (ii) permanent impairment of a body structure or a body function,
 - (iii) hospitalisation or prolongation of patient hospitalisation,
 - (iv) medical or surgical intervention to prevent life-threatening illness or injury or permanent impairment to a body structure or a body function,
 - (v) chronic disease,
- (c) foetal distress, foetal death or a congenital physical or mental impairment or birth defect.

Note: planned hospitalization for pre-existing condition, or a procedure required by the CIP, without a serious deterioration of the health status of the subject, is not considered an SAE

Device deficiency (Art. 2 Abs 59 MDR)

Inadequacy of a medical device related to its identity, quality, durability, reliability, safety or performance, of an investigational device, including malfunction, user errors and inadequate information supplied by the manufacturer. Device deficiency data will be collected by the blood banks and the clinic staff.

The blood bank teams will use the Hemanext ONE System to manufacture hypoxic RBCs. The Oslo blood bank will ship the hypoxic RBCs to the Bergen blood bank team for storage. Bergen blood bank team will confirm blood bag integrity prior to storage, when ordered for a subject and after each transfusion.

Malfunction (ISO14155)

Failure of an investigational device to perform in accordance with its intended purpose when used in accordance with the instructions for use or the CIP.

Device deficiency with Serious Adverse Device Effect (SADE) potential (Art. 80 Abs 1 letter c MDR; ISO14155)

Any device deficiency that might have led to a serious adverse event if appropriate action had not been taken, intervention had not occurred, or circumstances had been less fortunate.

Adverse Device Effect (ADE) (ISO14155)

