6.1 Safety Assessments

6.1.1 Assessment of Adverse Event and Adverse Device Effect

Patients will be monitored for Adverse Events (AE) and Adverse Device Effects (ADE) throughout the entirety of their participation in the clinical investigation from Visit 0 (Screening) to Visit 5 (Follow-Up 2). AEs and ADEs will be categorized as described in Section 6.1.2 to Section 6.1.12. Investigators will monitor patients directly for AEs and ADEs during their transfusion visit. In addition, patients will be contacted by phone at Visit 3 (24 hours post transfusion) and at Visit 4 (7 days (+/- 1)) after their transfusion visit to record any AEs and AEDs they have experienced since the transfusion Visit 2 (transfusion visit).

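### Burn patients enter as inpatients, but the 24-hour and Day 7 primary-outcome contacts are phone calls with no record review scheduled at either, so signs and laboratory AEs may be under-recorded or wrongly timed

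*Protocol*

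**What the plan says.** - **Outcome.** Protocol 7.1 defines the primary outcome as the "Number of participants who experienced an adverse event (all types/grades) within a time frame up to 24 hours following the transfusion". A second count covers the first week (7 days, +/- 1 day). Neither window is cut short by a further transfusion.
- **What counts.** The AE definition in Protocol 12.1 extends to "any untoward clinical signs (including an abnormal laboratory finding".
- **Who.** Burn criterion 3 in Protocol 9.1.1 reads "Smaller burn patients, hospitalized with a Total Body Surface Area (TBSA%) burn" of 10% to 50%. Criterion 2 requires that the patient can give consent personally.
- **Background.** The summary of potential benefits in Protocol 5.1.6 says of burn patients: "The clinical ramifications that may be observed include decreased organ dysfunction in these critically ill patients as well as reduction in thromboembolic events". It sets no rule for collecting AEs.
- **Scheduled contacts.** Protocol 11.2.1 has investigators observe the patient directly at the transfusion visit. It then adds the calls: "patients will be contacted by phone 24 hours and 7 days (+/- 1) after their transfusion visit to record any adverse events". Section 11.3.4 states: "This visit will occur 24 hours post-transfusion and will be performed over the phone". Section 11.3.5 sets the second contact at 7 days (+/- 1), "and will be performed over the phone". SAP 6.1.1 agrees: "patients will be contacted by phone at Visit 3 (24 hours post transfusion) and at Visit 4 (7 days (+/- 1". None of these has a variant for a patient still on the ward.
- **General sources.** The opening of Protocol 11.2 lists the patient, the medical record and, where applicable, a diary.
- **Chart check.** Protocol 11.2.2 and 11.3.6 place it at the next transfusion or Day 28, whichever is first. In 11.2.2 it comes under secondary outcomes.
- **AE record.** Protocol 12.2 and 12.6 ask for start and stop dates, and 12.8.1 for the onset date. No clock time is listed.
- **Schedule and end of collection.** In the burn schedule (Synopsis, Protocol 11.1.2, SAP Appendix B) the AE cell at Day 7 is blank and there is no diary row. Protocol 5.5 ends burn AE collection at discharge or Day 28.

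**The concern.** A phone call suits an outpatient. For someone on a ward, an abnormal laboratory result or a sign on the observation chart is known to staff and may never reach the patient, who cannot reliably report it. Such findings are AEs by the protocol's own definition and count towards the primary outcome at any grade.

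Complete ascertainment is this trial's main safeguard. It has 20 patients and no comparator, and SAP 8.1 drops the historical comparison. The sample-size argument in Protocol 13.2 relies on unexpected events being identified when they occur. Under-recording would make the product look better tolerated, in the group likely to have the fullest inpatient record. An event with an uncertain onset time can also move between the 24-hour count and the 7-day count.

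**Working it through.** There is no plan figure to reproduce: SAP 5.1 says the sample size has no statistical basis, and Protocol 13.1 states no hypothesis. The check is mainly a comparison of the collection rules.

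**1. What is scheduled for a burn patient**

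| Time | Scheduled contact | Record review scheduled there? |
|---|---|---|
| Transfusion visit | Direct observation (section 11.2.1) | Not specified |
| 24 hours | Call to the patient (section 11.3.4) | No |
| Day 7 (+/- 1) | Call to the patient (section 11.3.5), but AE cell blank in burn schedule | No |
| Next transfusion or Day 28 | Chart (section 11.3.6) | Yes |

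The record review named in 11.2 has no time point and no interval to cover.

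**2. Can the chart check close the 7-day window?** It can if the patient is not transfused again before Day 7, because events in the chart then carry dates. It need not if the patient is. Protocol 5.1.4 says post-operative bleeding can last for days and call for further transfusions. Take a further transfusion on Day 3 (my example). The chart check, which is also the final follow-up, then falls on Day 3. From there to Day 7 the only scheduled contact is the phone call, on a day when the burn schedule marks no AE collection.

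**3. Discharge.** Under Protocol 5.5, a burn patient whose AEs are still being collected is an inpatient. The call then reaches either a patient on the ward or one whose collection 5.5 has already ended. If discharge comes before Day 7, 5.5 stops collection inside the window of 7.1, whereas 11.2.2 and 11.3.6 continue.

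**4. The 24-hour split.** Let the transfusion be at clock hour *h*. An event dated to the next calendar day lies between 24 − *h* and 48 − *h* hours later. With *h* = 14 (my example) that is 10 to 34 hours. Since *h* is between 0 and 24, the 24-hour point always falls in this range, so a date alone cannot place the event. SAP 7.1.3 counts days and hours for assessments, but the AE items listed in the protocol do not supply an onset hour. This affects both patient groups and every AE source.

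**5. Size**

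- One affected burn patient left uncounted changes the burn rate by 1/10 = 10 percentage points and the total by 1/20 = 5 points. This applies only if the patient has no other recorded AE in that window.
- For illustration, let *p* be the true share of burn patients with a given AE and *c* the share of those captured. Both are assumptions. The chance of recording at least one affected patient among 10 is 1 − (1 − *pc*)^10:

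| *p* | *c* = 100% | 90% | 75% | 50% |
|---|---|---|---|---|
| 10% | 65.1% | 61.1% | 54.1% | 40.1% |
| 20% | 89.3% | 86.3% | 80.3% | 65.1% |

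For example, *p* = 0.10 and *c* = 0.75 give *pc* = 0.075, and one minus the tenth power of 0.925 is 0.541. The table shows direction and possible scale, and does not estimate this trial's loss.

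**The case against.** The best reply is that the protocol does not depend on the phone. Section 11.2 governs all outcome assessments and names the medical record; a general rule need not be repeated to apply. Section 11.2.1 adds direct observation at transfusion and presents the calls as additional. Sections 12.2 and 12.6 require all AEs to be documented from consent to the last procedure. The later chart check can recover dated ward events. SAP 7.8.1 defines its AE rows by time from transfusion and does not limit them to events found at Visit 3 or 4, so an event with Day 3 onset abstracted at Day 28 still counts. A ward record is also contemporaneous.

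All of this stands, and it limits the point. A reader might infer that primary-outcome AEs are collected by phone alone; the documents do not support that. It does not fill the gap, because 11.2 sets no duty to open the record at 24 hours or Day 7, the chart check can come before Day 7, and a dated entry need not settle the 24-hour split.

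A reader might also infer from Protocol 5.1.6 that the enrolled burn patients are too ill to answer a call. That passage concerns potential benefit. It mentions use in concomitant trauma, while 9.1.2 excludes combined trauma needing transfusion other than for the burn. The eligible patients have smaller burns and can consent for themselves.

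**Conclusion.** The concern holds in a limited form and should be acted on. The scheduled contacts at both primary time points are phone calls, with no inpatient variant and no record review, although burn patients enter hospitalised and AEs include signs and laboratory findings. The likely direction is under-recording in the burn group, together with uncertain placement around 24 hours.

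The size is unknown. It is tempting to assume an AE prevalence and a detection rate for a phone call and derive a number of missed patients. The documents give neither figure, and such a sum would give no credit to direct observation, general record use or the later chart check.

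The conclusion assumes that some burn patients are still in hospital at 24 hours or Day 7, since length of stay is not given, and that staff follow the visit sections as written. The blank Day 7 cell and the conflicting ends of collection need neither assumption.

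**What to change.** In Protocol 11.2.1, 11.3.4, 11.3.5 and SAP 6.1.1, state that for any patient still in hospital at 24 hours or Day 7 the visit is made in person. It includes review of the inpatient record (observations, laboratory results, operative charts) since the previous visit. The review runs through Day 7 even if a further transfusion comes earlier. Keep the phone call for discharged patients only.

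On the CRF, record AE onset date and time and the source of each AE (in person, record or phone), and show the source in the AE listing.

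Reconcile the blank Day 7 AE cell in the three burn schedules with 11.2.1 and 11.3.5. Reconcile the end of burn AE collection in 5.5 with 11.2.2 and 11.3.6, so that the 7-day window of 7.1 is covered.

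The cost is small: wording changes, corrected schedules and the added CRF items. Patients and charts are at the single study hospital, so no visits are added. There will be slightly more chart work and more AEs recorded in burn patients. The AE source will differ between inpatients and discharged patients, which the source field makes visible.
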